#### 10.7.2. Primary Efficacy Analysis

Unless otherwise specified, all primary efficacy analyses will be performed using the mITT population. Analyses of the primary endpoint of ADAS-Cog 13 will be performed with a likelihood based linear MMRM on treatment observed case (OC) data. The OC data set will consist of actual observations recorded at each visit during the double-blind treatment period and no missing data will be imputed. The model terms will include treatment, the stratification factors of use of concomitant AD medications (AChEI or none), age group (50 through 65 years or > 65 at the Screening – Part 1 Visit), gender, disease severity based on MMSE at the Baseline Visit, baseline ADAS-Cog 13 values, visit (VISIT), and treatment by visit interaction. The visit variable will be used to define the within-subject repeated measures over time. The least squares mean (LSM) for each treatment at each visit will be generated together with its 95% confidence interval, and the LSM difference between the active treatment and placebo will also be calculated; together

Confidential Page 94 of 115

with its standard error, and the 2-sided 95% confidence interval. For the primary endpoint at 78 weeks, treatment comparisons will be done at the 0.05 significance level.

All data collected during the study will be used in the statistical analysis. Additional details will be described in the final SAP. Sensitivity testing of the primary endpoint will include MMRM analyses for the PPP, and the CP.

For subjects who discontinue treatment prior to trial completion, every attempt will be made to have them continue with clinic visits and study assessments. Particular attention will be given to collecting Week 78 ADAS-Cog 13 assessments, regardless of when subjects discontinued treatment. These data from retrieved dropouts data will be used to impute missing data using multiple imputation method as a sensitivity analysis for the primary endpoint. This method assumes that the best reflection of what happened to the early dropout patients at Week 78 are the retrieved dropouts. For those subjects who terminate treatment prematurely but have Week 78 assessments, and the intermediate missing off-treatment data will be imputed by interpolation for analyses.

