4.1 Primary Clinical Outcome

The target study sample size was 300 subjects randomized or 150 subjects per treatment group, based on ADAS-Cog 13, the primary clinical outcome. The study completed enrollment with 325 randomized subjects. The ADAS-Cog 13 is a well-validated and widely-used measure of global cognition in AD observational studies and Phase 3 drug trials. This scale evaluates multiple cognitive domains including memory, language, praxis, orientation, and executive function. To improve the sensivity of ADAS-Cog in MCI patients, two additional items were added to the original 11-item scale, including delayed word recall and digit cancellation (Mohs 1997).

Study Sample Size

Sample size determination was based on ADAS-cog results from an AD trial with tramiprosate, the active agent in ALZ-801. These efficacy data were observed in Mild AD patients (baseline MMSE =22-26) with APOE4/4 genotype who received tramiprosate 150mg BID over 78 weeks (Abushakra 2017). The tramiprosate 150mg BID dose provides plasma exposures similar to ALZ-801 at 265mg BID, the dose used in the current study.

In the 78-week tramiprosate Phase 3 study, the APOE4/4 Mild AD patients showed approximately 5.0-point difference from placebo (benefit) on ADAS-Cog. Since this Phase 3

For the primary efficacy outcome of ADAS-Cog 13, this study is powered to detect a 3.0-point difference between the active ALZ-801 treatment and the placebo in the CBL to Week 78. An increase in ADAS-Cog scores denotes cognitive worsening. It is expected that the mean baseline ADAS-Cog 13 in both groups will be 22.0 (standard deviation [SD] 6.7), which is expected to increase by 6 points in placebo (CBL: 6.0, SD 5.6), and 3 points in the active drug arm (CBL: 3.0, SD 8.1). A sample size of 125 completed subjects per arm will provide > 90% power to detect a difference of 3 points on ADAS-Cog. The drop-out rate is estimated to be approximately 17% at 78 weeks, thus a total of 300 subjects enrolled would provide approximately 250 completers (125 per arm).

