ADAS-Cog 13 scores are assessed at Day 1 (Baseline), and Weeks 13, 26, 52 and 78. Observed ADAS-Cog 13 scores including those from unscheduled visits and early discontinuation, are assigned analysis visits based on the visit window using the assessment's study days. After applying a visit window, there is only one non-missing or missing value for each analysis visit. These data are called observed data and the change from baseline in ADAS-Cog 13 scores (observed data) for efficacy analyses are derived by subtracting corresponding baseline value at each visit. Other efficacy endpoints derivation follows the same algorithm.

Unless otherwise specified, all primary efficacy analyses will be performed using the FAS population. Analyses of the primary endpoint of ADAS-Cog 13 will be performed with a likelihood based MMRM on treatment observed cases (OCs). The observed data set will consist of actual observations recorded at each visit and missing data is not explicitly imputed. The model terms will include treatment, the stratification factors of use of concomitant AD medications (AChEI or none), age group (50-65 years inclusive or > 65 years through 80 years), gender, disease severity based on baseline MMSE (≤ 26 vs. > 26), baseline ADAS-Cog 13 values, visit (VISIT), and treatment-by-visit interaction. The visit variable will be used to define the within-subject covariance for the repeated measures over time. The least squares mean (LSM) for each treatment at each visit will be generated together with its 95% confidence interval, and the LSM difference between ALZ-801 and placebo will also be calculated; together with its standard error, and the 2-sided 95% confidence interval. The MMRM has an inherent mechanism to "implicitly impute" missing values when calculating the LSM of treatment effects which assume missing at random (MAR). For the primary endpoint at 78 weeks, treatment comparisons will be done at the 0.05 significance level.

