All data collected during the study will be used in the statistical analysis. Under the treatment policy strategy, measurements after occurrence of intercurrent events (subject withdrawal or dropouts for various reasons or use of symptomatic AD medications) will not be considered missing data and will be included in the primary analyses. For subjects who discontinue treatment prior to trial completion, every attempt will be made to have them continue with clinic visits and study assessments. Particular attention will be given to collecting Week 78 ADAS-Cog 13 assessments, regardless of when subjects discontinued treatment.

Note that only the post-baseline visits on which the endpoints are scheduled to be measured will be included in the model.

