8.3.2 Supportive and Sensitivity Analyses of the Primary Efficacy Endpoint

Supportive Analyses

As supportive analysis, the primary endpoint will be analyzed using the MMRM model on the per-protocol population and on completers. Additional supportive analyses may include MMRM with Last Observation Carried Forward (LOCF).

Additional supportive analyses will include the repetition of the primary analysis using the 'while-on-treatment' strategy on the FAS population. This strategy estimates the treatment effect before the occurrence of intercurrent events. These events include treatment discontinuation and the use of symptomatic AD medications (AChE inhibitors or memantine). Any data collected after the occurrence of intercurrent events will be considered as missing.

Sensitiviy Analyses

Multiple Imputations (Missing at Random, MAR)

As a sensitivity analysis, a similar MMRM model as the one applied to the primary endpoint analysis will be repeated using multiple imputation methods under the assumption of MAR.

Before conducting the multiple imputation, the missing data pattern will be examined. A dataset is said to have monotone missing pattern if the missing values always occur at the end of the longitudinal data, e.g., missing data after withdrawal.

A dataset is said to have non-monotone missing pattern if some subjects have missing values for intermediate visits but have available data at subsequent visits. If the ADAS-Cog data are deemed having monotone missing pattern, the standard multiple imputation approach using SAS PROC MI with regression method will be applied. If ADAS-Cog data are determined to have non-monotone missing pattern, the Markov Chain Monte Carlo (MCMC) method will first be applied to impute the intermittent missing data, and then the regression method will follow to impute the monotone missing data. In the case that the regression method cannot fully impute the missing data, the MCMC method will be applied to impute both monotone and non-monotone missing patterns. The example SAS programming codes using regression method for monotone missing pattern are:

```
PROC MI DATA=DATAIN OUT=DATAOUT NIMPUTE=100 SEED=999[to be changed]; CLASS TREATMENT ACHEI AGEGRP GENDER DISSTAGE; VAR TREATMENT ACHEI AGEGRP GENDER DISSTAGE BASE ...; [insert scheduled visits for ADAS-Cog 13 up to Week 78, i.e, V5 V7 ...] MONOTONE REGRESSION; RUN;
```

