Additional sensitivity analysis may be provided to evaluate the robustness of inferences on the same estimand, to assess deviations from the assumptions used in the statistical model, and to address limitations in the data. The possibility of "missing not at random" (MNAR) data will also be considered. After all active subjects complete the study and database is locked, the unblinded data will be examined and the missing data pattern evaluated. Based on the missing data mechanisms in the FAS, other multiple imputations methods will be explored to select the most appropriate methods. These methods may include the "Placebo-Based Pattern-Mixture model" or the "Tipping-Point Method". These sensitivity analyses will be described and documented in the final CSR.

Other Supportive or Sensitivity Analyses

Additional supportive or sensitivity analyses using observed data only (OC analysis), may be performed. For vMRI analyses, a model of slope analysis may also be conducted (Chen 2018; McDade 2022).

If any deaths occur, the worst-rank score method (Lachin 1999) will be employed as a supportive analysis. Any missing data due to deaths would be treated as the worst outcome in the primary analysis. This method makes no assumptions about the distribution. The observed changes from baseline at Week 78 in ADAS-Cog 13 scores from both the ALZ group and the placebo group will be combined and ranked from the lowest to the highest. Since a higher score in ADAS-Cog 13 indicates more severe impairment, the scores for all deaths will be assigned the highest rank. This analysis will be performed for the Week 78 observed cases data. The Wilcoxon Rank Sum Test and Hodges-Lehmann estimate will then be used to assess the treatment differences, and their 95% confidence intervals based on the Hodges-Lehmann estimates will also be provided.

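### SAP 8.3.2 chooses the missing-not-at-random sensitivity method after unblinding, and no committed analysis tests the missing-at-random assumption for subjects without a Week 78 score

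*SAP*

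**What the plan says.** SAP 8.3.2 opens its MNAR paragraph with an option: "Additional sensitivity analysis may be provided to evaluate the robustness of inferences on the same estimand". It then gives the timing: "After all active subjects complete the study and database is locked, the unblinded data will be examined and the missing data pattern evaluated". The selection step follows: "Based on the missing data mechanisms in the FAS, other multiple imputations methods will be explored to select the most appropriate methods". A placebo-based pattern-mixture model and a tipping-point method are named only as possibilities, without parameters, and the description is left to the clinical study report.

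The same section does commit to one imputation analysis, in which the primary model is "repeated using multiple imputation methods under the assumption of MAR". The primary MMRM in SAP 8.3.1 also assumes MAR.

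Protocol 10.7.2 had a different plan: "retrieved dropouts data will be used to impute missing data using multiple imputation method as a sensitivity analysis". The SAP does not carry this over and mentions retrieved dropouts only under disposition (7.1). Under its treatment-policy strategy (Table 16 and 8.3.1), scores after intercurrent events "will not be considered missing data and will be included in the primary analyses". Yet 8.3.1 also describes the primary MMRM as run on on-treatment observed cases, which read literally would leave those scores out.

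**The concern.** A sensitivity analysis supports a primary result only if its assumptions were fixed by people who could not see which assumptions suit the result. Here the one analysis that departs from MAR would be chosen with the treatment effect visible, from an open list, and it need not be done at all.

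Informative missingness is plausible in this trial. Protocol 5.5 allows withdrawal when cognition declines so far that consent or assent cannot continue, and requires it when memantine is judged necessary. The ADAS-Cog is given at Weeks 13, 26, 52 and 78, so decline between late visits may be caught only if an early-termination assessment is done. At stake is whether a reader could trust a statement that a positive result is robust to dropout. SAP 8.3.3 extends the same sensitivity set to the key secondary and other secondary endpoints.

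**Working it through.** **Which analyses test MAR for subjects with no Week 78 score?**

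- MAR multiple imputation (committed): same assumption as the MMRM, so it is a check on implementation and not on the assumption.
- While-on-treatment (committed): sets more data to missing under the same model.
- Per-protocol and completer analyses (committed): change the population.
- Worst-rank (if deaths occur): covers deaths only.
- MMRM with last observation carried forward (optional in 8.3.2 and 8.3.3): departs from MAR, but at one fixed and weak point in a progressive disease; it does not vary the assumption systematically.
- Pattern-mixture or tipping-point: optional, chosen after unblinding.

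No committed analysis does the job.

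**Reproducing the plan's power (SAP 4.1).** SDs 8.1 (active) and 5.6 (placebo), 125 completers per arm, two-sided 0.05. The sum of variances is 8.1² + 5.6² = 96.97, so SE = √(96.97/125) = 0.881. For 3.0 points, z = 3.41 and power is 92.6% (stated: above 90%). For 2.5 points, z = 2.84 and power is 81.0% (stated: about 80%). The inputs reproduce.

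**How far could the method matter?** SAP 4.1 reports: "The study completed enrollment with 325 randomized subjects". That is 162.5 per arm. Let m be the fraction of Week 78 scores missing, equal in both arms.

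- n = 162.5 × (1 − m); SE = √(96.97/n); significance boundary = 1.96 × SE.
- Placebo-based imputation with no retained benefit: effect becomes (1 − m) × observed effect.
- Results that lose significance: from the boundary to boundary/(1 − m).

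| m | n per arm | SE | Band (points) | 3.0 becomes | 2.5 becomes | 2.0 becomes |
|---|---|---|---|---|---|---|
| 17% (planned dropout, none retrieved) | 134.9 | 0.848 | 1.66 to 2.00 | 2.49 (p = 0.003) | 2.08 (p = 0.014) | 1.66 (p from 0.018 to 0.050) |
| 8.5% (half retrieved) | 148.7 | 0.808 | 1.58 to 1.73 | 2.75 (p < 0.001) | 2.29 (p = 0.005) | 1.83 (p from 0.013 to 0.023) |

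The windows in SAP 8.2.1 (Table 5) count early-termination ADAS-Cog scores from day 457 as Week 78. If dropout is uniform over time (assumption), m = 0.17 × 456/547 = 14.2%, n = 139.5, SE = 0.834, and the band is 1.63 to 1.90.

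**Unequal dropout.** With 22% missing on active and 12% on placebo (assumption; average 17%), n = 126.75 and 143. SE = √(65.61/126.75 + 31.36/143) = 0.858, the boundary is 1.68, and the band runs to 1.68/0.78 = 2.16. The planning effects become 2.34 (z = 2.73) and 1.95 (z = 2.27), still significant.

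**Chance of landing in the band**, Φ((upper − d)/SE) − Φ((lower − d)/SE): at 17% missing, about 6% for a true effect d of 3.0 and 12% for 2.5; at 8.5%, about 2% and 4%.

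**Tipping shift** for missing active-arm scores, (effect − boundary)/m: for an observed 3.0 points, 7.9 points at 17% and 16.7 at 8.5%; for 2.5 points, 4.9 and 10.8.

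Imputation variance is not modelled. All 325 are used as the base, although the full analysis set requires a post-baseline efficacy assessment (SAP 6.1).

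**The case against.** The case for leaving the text alone is reasonable. Sensitivity analyses carry no alpha. Both planning effects survive placebo-based imputation, and on those effects a result in the affected band is unlikely. SAP sections 1 and 8.1 require deviations and changes to be documented in the clinical study report, so a late choice would be visible. All of this stands and limits the weight of the point. But disclosure after the fact is not pre-specification, and naming one method beforehand is cheap.

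A reader might infer that the SAP broke a protocol commitment by abandoning retrieved-dropout imputation. The documents support less. Protocol 10.7.2 paired that imputation with an on-treatment primary analysis and left further details to the SAP. Under treatment policy, retrieved scores enter the primary model directly, and the open list in 8.3.2 does not exclude the method. What remains is secondary: the SAP does not carry the analysis over or say why, and treatment policy does nothing for subjects who were not retrieved.

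A reader might also infer that the primary p-value or family-wise error is compromised. It is not: the primary model, endpoint and test level are set out in 8.3.1, and the MNAR paragraph does not alter them.

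**Conclusion.** The point holds as a weakness in the robustness evidence and should be corrected before unblinding. SAP 8.3.2 states a rule for choosing the MNAR method on unblinded data, and nothing else that is committed tests MAR for subjects without a Week 78 score. The practical effect is confined to borderline results: roughly 1.66 to 2.00 points at 17% missing and 1.58 to 1.73 at 8.5%.

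Those figures rest on equal missingness by arm, no retained benefit in missing active-arm subjects, the planning SDs and a normal approximation. It would be tempting to read the 17% band as a worst case. It is not a strict bound: unequal dropout moves its upper end to 2.16, and Week 78 scores missing in subjects who did not drop out (a missed visit, or more than three missing ADAS-Cog 13 items under SAP 8.2.4) are not counted. The 8.5% case also applies only if treatment policy, and not the on-treatment wording in 8.3.1, governs the primary analysis.

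**What to change.** In SAP 8.3.2, delete the sentences that select the method after unblinding. Commit, before unblinding, to:

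1. Placebo-based pattern-mixture multiple imputation of missing Week 78 values.
2. A delta-adjusted tipping-point analysis that worsens missing ALZ-801 Week 78 values step by step until significance is lost at the alpha in force for that endpoint: 0.05 for ADAS-Cog 13, and 0.025 or 0.05 under SAP 8.1.5 for A-IADL-W and CDR-SB.

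Any review of missing-data patterns before these choices are final should be pooled and blinded. Reconcile the on-treatment observed-case wording in 8.3.1 with the treatment-policy strategy in Table 16 and 8.3.1, so that it is clear which Week 78 scores count as missing. Keep the MAR imputation as a check on the MMRM.

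Retrieved-dropout imputation can stay as an optional further analysis if enough subjects are retrieved. The retrieved-dropout visit in Protocol 7.2.15 does not include the CDR, so it could not be relied on for CDR-SB.

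The cost is SAP text and some extra programming, with no new data. The sponsor gives up choosing the method later; further post hoc analyses remain possible if labelled as such.

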3 STUDY OVERVIEW

3.1 Study Design

This is a Phase 3, multicenter, randomized, double-blind, placebo-controlled, parallel-group, two-arm study, with a treatment duration of 78 weeks (18 months). Randomization will be stratified by use of concomitant AD medications (AChEI or none), age (50-65 years inclusive, or >65 years), gender, and by disease stage at screening (low versus high MMSE groups). Based on the screening MMSE, it is expected that approximately 60% will be AD subjects with MMSE 22-26 (inclusive), and approximately 40% will be AD subjects with MMSE 27-30 (inclusive).

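### The worst-rank analysis for deaths uses a rank test without baseline ADAS-Cog 13 or the stratification factors as covariates; adjusting it would be a cheap but minor gain in precision

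*SAP*

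**What the plan says.** SAP 8.3.2, under other supportive or sensitivity analyses, commits to a worst-rank method that "will be employed as a supportive analysis" if any deaths occur. The ranked quantity is a change score: "The observed changes from baseline at Week 78 in ADAS-Cog 13 scores" from both arms are pooled and ranked, and deaths take the highest (worst) rank. On the data set it says "This analysis will be performed for the Week 78 observed cases data". The comparison is then specified as "The Wilcoxon Rank Sum Test and Hodges-Lehmann estimate will then be used to assess the treatment differences", with a 95% interval from the Hodges-Lehmann method. No covariate, stratified rank test or rank ANCOVA is named.

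SAP 3.1 gives the design: "Randomization will be stratified by use of concomitant AD medications (AChEI or none), age (50-65 years inclusive, or >65 years), gender", and also MMSE stage. The primary MMRM in SAP 8.3.1 carries all four stratification factors as well as "baseline ADAS-Cog 13 values, visit (VISIT), and treatment-by-visit interaction". SAP 3.3 says that the as-randomised factors go into the statistical models, which does not clearly reach a two-sample rank-sum test.

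**The concern.** The rest of the confirmatory and supportive modelling adjusts. The multiple-imputation code in SAP 8.3.2, the secondary-endpoint MMRMs in 8.3.3, the Cox models in 8.3.6.1 and the biomarker MMRMs in 8.4 all use the four factors, and the MMRMs also use the relevant baseline value. The deaths analysis of the primary endpoint is specified without them.

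It is also the only analysis the SAP firmly specifies for this endpoint that scores death as the worst outcome. The MMRM treats values missing after death as missing at random, and the MNAR methods in 8.3.2 are optional and chosen after unblinding. If the MMRM were significant and the worst-rank test were not, a reader would want to know whether the deaths explain it. Lost precision from omitted prognostic covariates adds a second explanation that could be avoided.

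**Working it through.** **Inputs.** From SAP 4.1: change SD 8.1 (active) and 5.6 (placebo), 125 completers per arm, differences of 3.0 and 2.5 points. From SAP 8.1.2: two-sided 0.05. The documents give neither the correlation between baseline and change (rho) nor the share of variance explained by all the covariates (R²), so both are varied.

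**The plan's own power first.** Root-mean-square SD = √((8.1² + 5.6²)/2) = 6.963. SE = √((8.1² + 5.6²)/125) = 0.881. Power = Φ(δ/SE − 1.96).
- δ = 3.0: Φ(3.406 − 1.96) = 92.6%, against the SAP's figure of over 90%.
- δ = 2.5: Φ(2.838 − 1.96) = 81.0%, against the SAP's approximate 80%.

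Both agree. The documents state no power for the worst-rank test itself.

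**Plain and adjusted rank test, approximation.** With Wilcoxon efficiency 0.955 relative to the t-test, power = Φ((δ/SE)·√(0.955/(1 − R²)) − 1.96). Setting R² = 0 gives the plain test: 91.4% at 3.0 points and 79.2% at 2.5. At R² = 0.20 and δ = 2.5, the first term is 2.774/0.894 = 3.101, which gives 87.3%.

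**Simulation 1: baseline only, no deaths, 6,000 trials per setting.** Power (%), plain Wilcoxon → rank ANCOVA:

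| rho (assumed) | 2.5 points | 3.0 points |
|---|---|---|
| 0.2 | 78.7 → 79.8 (+1.1) | 91.0 → 91.9 (+0.9) |
| 0.3 | 78.6 → 81.5 (+2.9) | 90.9 → 92.7 (+1.8) |
| 0.4 | 78.8 → 84.3 (+5.5) | 90.5 → 94.1 (+3.6) |
| 0.5 | 79.1 → 88.5 (+9.4) | 90.7 → 96.0 (+5.3) |

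Type I error was 5.0 to 5.8% for both tests.

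**Simulation 2: baseline plus the four factors, randomisation balanced within strata, 4,000 trials per setting.** R² is split equally between baseline and the factors. Power (%), plain → adjusted:

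| R² (assumed) | 2.5 points | 3.0 points | Type I error, plain (%) |
|---|---|---|---|
| 0 | 78.1 → 78.0 | 90.8 → 90.6 | 5.5 |
| 0.10 | 79.9 → 82.2 | 91.0 → 92.6 | 4.8 |
| 0.20 | 79.1 → 84.9 | 92.0 → 95.8 | 4.2 |
| 0.30 | 79.0 → 89.7 | 92.5 → 97.0 | 3.7 |

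The adjusted test stayed at 5.2 to 5.5%. So the plain test drifts below its nominal level when the randomisation is balanced on factors that predict outcome and the test ignores that balance.

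**With deaths.** The analysis runs only if someone dies, so two deaths per arm were added at the worst rank (an assumed number, with deaths unrelated to the covariates). In the second set-up at R² = 0.20, power was 77.3 → 83.6% at 2.5 points and 90.4 → 94.3% at 3.0. The gain persists.

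**The case against.** The strongest reply is that this is a choice between two valid tests, and that no decision depends on it. The worst-rank analysis is supportive, conditional on deaths, and outside the alpha-controlled procedure of SAP 8.1.5. The Wilcoxon and Hodges-Lehmann pair gives a test, an estimate and an interval from one framework, whereas a rank ANCOVA p-value would sit beside an unadjusted interval that can disagree with it. Power is also not short. With 325 randomised (SAP 4.1) and 17% dropout, 325 × 0.83/2 ≈ 135 per arm remain, and the plain Wilcoxon test without deaths then has about 82% power at 2.5 points and 93% at 3.0. All of this stands, and it is why the point is minor.

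A reader might infer that the missing covariates are what makes the result not comparable with the primary model. The documents do not support that. The worst-rank analysis uses Week 78 observed cases, scores death as worst and reports a Hodges-Lehmann shift. The primary analysis is a repeated-measures model over all scheduled visits that reports a least-squares mean difference. Those differences remain after adjustment, so a discordant pair of results would still need interpretation.

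A reader might also infer that baseline is ignored altogether, or that every subject has all five covariates. Neither holds. Change from baseline is what is ranked, so baseline is subtracted and is only absent as a covariate. Entry to the full analysis set (SAP 6.1) requires some baseline assessment, not specifically ADAS-Cog 13, and SAP 8.2.3 never imputes a missing baseline score. A subject who died without a baseline ADAS-Cog 13 could take the worst rank in the planned test but would drop out of an adjusted one. This is probably rare.

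What the reply does not remove is that baseline scores and randomisation strata are collected anyway, and using them costs almost nothing.

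**Conclusion.** The point holds as a minor, nearly free improvement. The planned test is valid, with no material inflation of type I error, and is somewhat conservative under stratified randomisation if the factors are prognostic. It gives up about 1 to 9 points of power at a 2.5-point difference and about 1 to 5 points at 3.0 points. These ranges rest on 125 per arm, SDs of 8.1 and 5.6, and an assumed rho of 0.2 to 0.5; the loss at 2.5 points reaches 5 points only when rho is about 0.4 or more. With the four factors added, the same conclusion holds over R² of 0.10 to 0.30, and the loss is nil at R² = 0.

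It would be a mistake to read this as a flaw that threatens the primary conclusion. The primary MMRM is already adjusted, and nothing in the testing procedure depends on the worst-rank result.

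**What to change.** In SAP 8.3.2, keep the worst-rank assignment for deaths. Replace the test with a rank ANCOVA: regress the ranks of the Week 78 change on ranked baseline ADAS-Cog 13 and the four as-randomised stratification factors (the SAP 3.3 convention), and compare the residuals between arms. Report the unadjusted Wilcoxon test and the Hodges-Lehmann estimate with its 95% interval alongside. Settle this before unblinding, because SAP 8.1 otherwise leaves room to change methods at the final analysis.

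A stratified van Elteren test is an alternative, but it does not use baseline. Four two-level factors also give 2⁴ = 16 cells, or about 250/16 ≈ 16 completers per cell on average, so some cells would be sparse.

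The cost is two sentences, a few lines of code and no new data. There are two drawbacks to state in the text: the adjusted p-value has no matching Hodges-Lehmann interval, and a subject without a baseline ADAS-Cog 13 enters only the unadjusted companion analysis.
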